5.1.2. Additional Inclusion Criteria for Group 1 *Only* (without HI)

1. At screening, no clinically relevant abnormalities identified by a detailed medical history, complete PE, including BP and pulse rate measurement, 12-lead ECG and clinical laboratory tests, as assessed by the sponsor approved laboratory.
2. At screening, participants must meet the demographic-matching criteria, including:
 - A body weight that is within ± 15 kg of the average of the pooled hepatic impairment groups (Groups 2-4), as provided by the sponsor;
 - An age that is within ± 10 years of the average of the pooled hepatic impairment groups (Groups 2-4), as provided by the sponsor;
 - *Attempts will be made* to ensure that the male-to-female distribution in Group 1 is comparable to that in the pooled hepatic impairment groups (Groups 2-4).
3. No known or suspected hepatic impairment, and meet all the following criteria at screening, as assessed by the sponsor approved laboratory, with a single repeat permitted to assess eligibility, if needed:
 - ALT \leq ULN;
 - AST \leq ULN;
 - T bili \leq ULN.

NOTE: Participants with a history of Gilbert syndrome (and hence elevated T bili) are eligible provided direct bilirubin level is \leq ULN plus ALT and AST are \leq ULN plus alkaline phosphatase, hemoglobin, and reticulocyte count are all \leq ULN.

- Albumin \leq ULN;
- PT \leq ULN.

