5.2.3. Additional Exclusion Criteria for Groups 2-4 Only (Mild, Moderate, and Severe HI)

1. Hepatic carcinoma or hepatorenal syndrome or limited predicted life expectancy (defined as <1 year).
2. A diagnosis of hepatic dysfunction secondary to any acute ongoing hepatocellular process that is documented by medical history, PE, liver biopsy, hepatic ultrasound, CT scan, or MRI.
3. History of gastrointestinal hemorrhage due to esophageal varices or peptic ulcers less than **4 weeks** prior to the screening visit.
4. Signs of clinically active Grade 3 or 4 hepatic encephalopathy (ie, >Grade 2 Portal Systemic Encephalopathy score; refer to [Appendix 10](#)).
5. Severe ascites and/or pleural effusion, except for those categorized in Group 4 who may be enrolled provided participant is medically stable, per the investigators' medical judgment.
6. Previously received a kidney, liver, or heart transplant.
7. Screening supine 12-lead ECG demonstrating a QTcF interval >470 ms or a QRS interval >120 ms. If QTcF exceeds 470 ms, or QRS exceeds 120 ms, the ECG should be repeated 2 more times and the average of the 3 QTcF or QRS values should be used to determine eligibility.
8. At screening, Day -1 or pre-dose on Day 1, persistent severe, uncontrolled hypertension as outlined below:
 - **Seated** SBP \geq 180 mmHg or DBP \geq 105 mmHg after \geq 5 minutes of seated rest, with a single repeat permitted to assess eligibility, if needed, at each of these 2 visits; if done, the repeat assessment overrides initial results.

NOTE: For participants with SBP \geq 160 and \leq 179 mmHg or DBP \geq 100 and \leq 104 mmHg at screening, the period between screening and Day 1 may be used to refine the doses of the agents used for management of BP with the aim of having stable BP by Day -1.

 - **Day 1:** seated SBP \geq 160 mmHg or DBP \geq 100 mmHg after \geq 5 minutes of seated rest, with a single repeat permitted to assess eligibility, if needed; if done, the repeat assessment overrides initial results.
9. ALT or AST >5 x ULN on clinical laboratory tests at screening, as assessed by the sponsor approved laboratory, with a single repeat permitted to assess eligibility, if needed.

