8.3.4. Clinical Safety Laboratory Assessments

See [Appendix 2](#) for the list of clinical safety laboratory tests to be performed and the **SoA** for the timing and frequency. All protocol-required laboratory assessments, as defined in [Appendix 2](#), must be conducted in accordance with the laboratory manual and the **SoA**. Unscheduled clinical laboratory measurements may be obtained at any time during the study to assess any perceived safety issues.

The investigator must review the laboratory report, document this review, and record any clinically significant changes occurring during the study in the AE section of the CRF. Clinically significant abnormal laboratory test findings are those that are not associated with the underlying disease, unless judged by the investigator to be more severe than expected for the participant's condition.

All laboratory tests with values considered clinically significant and abnormal during participation in the study or within 5 days after the last dose of study intervention should be repeated until the values return to normal or baseline or are no longer considered clinically significant by the investigator or study medical monitor.

If such values do not return to normal/baseline within a period of time judged reasonable by the investigator, the etiology should be identified and the sponsor notified.

See [Appendix 6](#) for suggested actions and follow-up assessments in the event of potential DILI.

See [Appendix 7](#) for instructions for laboratory testing to monitor kidney function and reporting laboratory test abnormalities.

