10.3.1. Definition of AE

| AE Definition |
|---|
| 
• An AE is any untoward medical occurrence in a patient or clinical study participant, temporally associated with the use of study intervention, whether or not considered related to the study intervention.• Note: An AE can therefore be any unfavorable and unintended sign (including an abnormal laboratory finding), symptom, or disease (new or exacerbated) temporally associated with the use of study intervention. |

| Events Meeting the AE Definition |
|---|
| 
• Any abnormal laboratory test results (hematology, clinical chemistry, or urinalysis) or other safety assessments (eg, ECG, radiological scans, vital sign measurements), including those that worsen from baseline, considered clinically significant in the medical and scientific judgment of the investigator. Any abnormal laboratory test results that meet any of the conditions below must be recorded as an AE:
• Is associated with accompanying symptoms;• Requires additional diagnostic testing or medical/surgical intervention;• Leads to a change in study dosing (outside of any protocol-specified dose adjustments) or discontinuation from the study, significant additional concomitant drug treatment, or other therapy.• Exacerbation of a chronic or intermittent preexisting condition, including an increase in either frequency and/or intensity of the condition.• New condition detected or diagnosed after study intervention administration, even though it may have been present before the start of the study. |

- Signs, symptoms, or the clinical sequelae of a suspected drug-drug interaction.
- Signs, symptoms, or the clinical sequelae of a suspected overdose of either study intervention or a concomitant medication. Overdose per se will not be reported as an AE or SAE unless it is an intentional overdose taken with possible suicidal/self-harming intent. Such overdoses should be reported regardless of sequelae.

Events NOT Meeting the AE Definition

- Any clinically significant abnormal laboratory findings or other abnormal safety assessments that are associated with the underlying disease, unless judged by the investigator to be more severe than expected for the participant's condition.

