 - Preexisting AST or ALT baseline values above the normal range: AST or ALT values ≥ 2 times the baseline values AND $\geq 3 \times$ ULN; or $\geq 8 \times$ ULN (whichever is smaller).
 - Preexisting values of T bili above the normal range: T bili level increased from baseline value by an amount of $\geq 1 \times$ ULN **or** if the value reaches $\geq 3 \times$ ULN (whichever is smaller).

Rises in AST/ALT and T bili separated by more than a few weeks should be assessed individually based on clinical judgment; any case where uncertainty remains as to whether it represents a potential Hy's law case should be reviewed with the sponsor.

The participant should return to the investigator site and be evaluated as soon as possible, preferably within 48 hours from awareness of the abnormal results. This evaluation should include laboratory tests, detailed history, and physical assessment.

In addition to repeating measurements of AST and ALT and T bili for suspected Hy's law cases, additional laboratory tests should include albumin, CK, direct and indirect bilirubin, GGT, PT/INR, total bile acids, and alkaline phosphatase. Consideration should also be given to drawing a separate tube of clotted blood and an anticoagulated tube of blood for further testing, as needed, for further contemporaneous analyses at the time of the recognized initial abnormalities to determine etiology. A detailed history, including relevant information, such as review of ethanol, acetaminophen/paracetamol (either by itself or as a co-formulated product in prescription or over-the-counter medications), recreational drug, or supplement (herbal) use and consumption, family history, sexual history, travel history, history of contact with a jaundiced person, surgery, blood transfusion, history of liver or allergic disease, and potential occupational exposure to chemicals, should be collected. Further testing for acute hepatitis A, B, C, D, and E infection, liver imaging (eg, biliary tract), and collection of serum samples for acetaminophen/paracetamol drug and/or protein adduct levels may be warranted.

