#### 3.5.2. Laboratory Data

Safety laboratory tests will be performed as described in the protocol. To determine if there are any clinically significant laboratory abnormalities, the haematological and clinical chemistry will be assessed against the criteria specified in the sponsor reporting standards. The assessment will not take into account whether each participant's baseline test result is within or outside the laboratory reference range for the particular laboratory parameter.

The baseline measurement is the predose measurement on Day 1. Changes from baseline will be defined as the change between the postdose and baseline measurements.

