### **6.6.2. Laboratory Data**

Laboratory data will be listed and summarized by hepatic function group in accordance with the CaPS.

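### The laboratory abnormality flag in SAP 3.5.2 disregards baseline status, so by-group counts can differ with no post-dose change, and SAP 6.6.2 names no change or shift output

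*SAP*

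**What the plan says.** SAP 3.5.2 states that "the haematological and clinical chemistry will be assessed against the criteria specified in the sponsor reporting standards". It adds that this assessment takes no account of whether the "baseline test result is within or outside the laboratory reference range for the particular laboratory parameter". The same section sets the Day 1 pre-dose value as baseline and defines change from baseline.

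On output, SAP 6.6.2 says only: "Laboratory data will be listed and summarized by hepatic function group in accordance with the CaPS". SAP 5.2.1 presents categorical criteria as numbers and percentages of participants. Laboratory abnormalities are part of the secondary endpoint in SAP 2.2.

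The entry rules differ by group:
- Group 1 (Protocol 5.1.2, item 3): "No known or suspected hepatic impairment, and meet all the following criteria at screening". The list that follows puts ALT, AST and total bilirubin at or below ULN, with an exception for Gilbert syndrome.
- Groups 2-4 (Protocol 5.2.3, item 9): exclusion applies only when ALT or AST is more than five times "ULN on clinical laboratory tests at screening". There is no numeric upper limit for bilirubin. Group assignment uses bilirubin, albumin and PT through the Child-Pugh score (Protocol Appendix 10, Table 8).

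**The concern.** A flag that ignores baseline does little harm when all groups start from similar values. Here the groups are formed on liver function. For a liver test, a higher count in the moderate or severe group could reflect the disease that put participants there, a post-dose change, or both, and the count alone does not say which.

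The liver tests are also where a drug signal would be sought. Protocol 2.2.3 names the hepatobiliary system as the key target organ in adult animals, with raised ALP, ALT and GGT in dogs. Protocol 2.3.1 gives laboratory monitoring of transaminases, ALP and GGT as the mitigation. At stake is whether the by-group laboratory summary can be read as evidence about the drug.

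**Working it through.** The plan gives no figure to reproduce here, because the point concerns a reporting rule. The check asks what the entry rules allow before dosing.

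**1. ALT and AST.** The inputs are the Group 1 ceiling of 1x ULN (Protocol 5.1.2) and the Groups 2-4 ceiling of 5x ULN (Protocol 5.2.3). Take a sponsor limit of L x ULN, with a flag when the value exceeds it.
- L above 1 and below 5: the limit can already be exceeded at screening in Groups 2-4 but not in Group 1.
- L of 5 or more: it cannot be exceeded at screening in any group, so the problem does not arise there.

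**2. Total bilirubin.** Group 1 is held at or below ULN, Gilbert exception aside, and Groups 2-4 have no numeric ceiling. Any limit above ULN can therefore be exceeded before dosing in Groups 2-4.

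**3. Albumin.** The Group 1 criterion is an upper bound and does not by itself rule out a low value. The link to group runs through Child-Pugh, where albumin of 2.8 to 3.5 g/dL scores 2 points and below 2.8 scores 3.

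**4. What the flag can and cannot show** (illustrative values).
- Bilirubin of 3.5 mg/dL before dosing, limit below 3.5: a post-dose value of 3.5 gives one flag, and a post-dose value of 7.0 also gives one flag.
- ALT rising from 2x to 4x ULN, limit 3x ULN: the participant starts abnormal but below the limit, so the rise produces a new flag.

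The loss of information is thus confined to participants already beyond the limit before dosing.

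**5. Child-Pugh scores that can enter.** Active Grade 3-4 encephalopathy is excluded, so that item scores 1 or 2; the other four items score 1 to 3.
- Permitted combinations: 2 x 3 x 3 x 3 x 3 = 162, of which 81 are Class C.
- Highest total with bilirubin, albumin and PT all at 1 point: 2 + 3 + 1 + 1 + 1 = 8, below the 10 needed for Class C.
- The only Class C combination with both bilirubin and albumin at 1 point: 2 + 3 + 1 + 1 + 3 = 10.
- So 80 of 81 Class C combinations have bilirubin or albumin above the 1-point band.

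These are combinations of scores, not patients and not flags.

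**6. Size under an assumption.** Let p be the share of Group 4 already beyond a limit before dosing and unchanged afterwards. The documents do not give p. With no drug effect, the expected number of participants flagged is n x p, and the chance of at least one is 1 - (1 - p)^n.

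| p (assumed) | n = 4: expected; chance of at least one | n = 8: expected; chance of at least one |
|---|---|---|
| 0 | 0; 0 | 0; 0 |
| 0.25 | 1; 0.68 | 2; 0.90 |
| 0.50 | 2; 0.94 | 4; 0.996 |
| 0.75 | 3; 0.996 | 6; >0.999 |

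**The case against.** The strongest reply is that the plan does not ignore baseline altogether.
- **Change from baseline is defined** in SAP 3.5.2. This stands, and it narrows the point: the gap is that 6.6.2 names no output using the defined variable.
- **Listings show each participant's values.** With one routine post-dose laboratory time (Day 6 or early termination) and about 28-34 participants, a reader can compare before and after by hand. This stands as a backstop, but it is not a by-group summary.
- **Worsening can be an adverse event.** Protocol 10.3.1 covers abnormal results, "including those that worsen from baseline, considered clinically significant in the medical and scientific judgment of the investigator". That depends on judgement, and the same section leaves out findings associated with the underlying disease unless more severe than expected.
- **Appendix 6 adjusts for baseline**, for example: "Preexisting values of T bili above the normal range: T bili level increased from baseline value by an amount of" at least 1x ULN. Those thresholds identify potential drug-induced liver injury from AST or ALT together with bilirubin. They do not cover a rise in ALP or GGT alone, and the SAP names no table based on them.
- **CaPS may already give baseline-aware tables.** This cannot be checked. If so, naming them is enough.

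A reader might also infer that the SAP contradicts Protocol 8.3.4, which says: "Clinically significant abnormal laboratory test findings are those that are not associated with the underlying disease". The documents do not support that. The protocol text governs what investigators record as adverse events, while the SAP ties its assessment to sponsor criteria. Two rules with different purposes can differ without conflict.

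**Conclusion.** The point holds as a limitation of one descriptive summary. Under the entry rules, flags for ALT, AST (for limits between 1x and 5x ULN) and bilirubin (for any limit above ULN) can differ between Group 1 and Groups 2-4 with no post-dose change. In participants already past the limit, the count does not separate stable from worse.

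This rests on three assumptions:
- The flags are tabulated by group. This is inferred from SAP 5.2.1 and 6.6.2, as no such table is named.
- Some sponsor limits fall within the ranges above.
- Screening values broadly persist to Day 1, since the entry limits apply at screening, up to 28 days before dosing, and baseline is Day 1 pre-dose.

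The number of affected flags is unknown. Two stronger readings are tempting, and neither is supported. One is that the count hides worsening in everyone who starts abnormal; it does so only for those already beyond the limit. The other is that the 80 of 81 Class C combinations mean that nearly all of Group 4 would be flagged. A scored bilirubin or albumin says nothing about an undisclosed sponsor limit, and score combinations are not patient frequencies.

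No hypothesis is tested, and the primary PK comparison is unaffected. The change is worth making because it is cheap and the tests concerned are those of most interest for this drug.

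**What to change.** In SAP 3.5.2 and 6.6.2:
- Keep the existing abnormality count, but present it by hepatic function group split by normal or abnormal Day 1 pre-dose value.
- Add, by hepatic function group, a shift or change-from-baseline summary from Day 1 pre-dose to Day 6 or early termination for total bilirubin, albumin, ALT, AST, ALP and GGT. Take worsening as a fall for albumin and a rise for the others.
- Say whether PT is covered, since SAP 3.5.2 names only haematology and chemistry while the protocol lists PT under coagulation. If it is, include it.
- If CaPS already produces these tables, name them in 6.6.2; nothing more is then needed.

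The cost is SAP wording and one or two extra descriptive tables, with no new samples or visits. Cells will be small, with 4 to 10 participants per group before the split, so the tables should be read alongside the listings.

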#### 3.5.3. Vital Signs

Seated blood pressure (BP) and pulse rate (PR) will be measured at times specified in the SoA given in the protocol.

The baseline measurement is the predose measurement on Day 1. Changes from baseline will be defined as the change between the postdose and baseline measurements.

### 3.5.4. Electrocardiograms

QT interval, QTcF, PR, QRS and HR will be recorded at each assessment time indicated in the SoA given in the protocol. If not supplied, QTcF will be derived using Fridericia's heart rate correction formula:

$$\text{QTcF} = \text{QT} / (\text{RR})^{(1/3)} \text{ where RR} = 60/\text{HR} \text{ (if not provided)}$$

The baseline measurement is the predose measurement on Day 1. Changes from baseline will be defined as the change between the postdose and baseline measurements.

## 4. ANALYSIS SETS (POPULATIONS FOR ANALYSIS)

Data for all participants will be assessed to determine if participants meet the criteria for inclusion in each analysis population prior to releasing the database and classifications will be documented per standard operating procedures.

Participant Analysis Set	Description
Enrolled	“Enrolled” means a participant’s, or their legally authorized representative’s, agreement to participate in a clinical study following completion of the informed consent process and assignment to study intervention. A participant will be considered enrolled if the informed consent is not withdrawn prior to participating in any study activity after screening. Potential participants who are screened for the purpose of determining eligibility for the study, but do not participate in the study, are not considered enrolled, unless otherwise specified by the protocol.
Safety analysis set	All participants assigned to study intervention and who take at least 1 dose of study intervention.
PK Concentration Set	The PK concentration population is defined as all participants who received at least 1 dose of PF-07923568 and in whom at least 1 plasma concentration value is reported.
PK Parameter Set	The PK parameter analysis population is defined as all participants who received at least 1 dose of PF-07923568 and have at least 1 of the PK parameters of interest calculated.

## 5. GENERAL METHODOLOGY AND CONVENTIONS

Final analysis will be performed after study participant data set release following last participant last visit.

## 5.1. Hypotheses and Decision Rules

No statistical hypothesis will be tested in this study.

## 5.2. General Methods

### 5.2.1. Analyses for Binary/Categorical Endpoints

For binary or categorical variables, number and percentages of participants meeting the categorical criteria will be presented in accordance with the Clinical Data Interchange Standards Consortium and Pfizer Standards (CaPS).

### 5.2.2. Analyses for Continuous Endpoints

For continuous variables, the data will be summarized using the number of participants, mean, standard deviation (SD), median, minimum, and maximum in accordance with the CaPS. For appropriate PK parameters, geometric mean and geometric coefficient of variation (%CV) will also be summarized.

## 5.3. Methods to Manage Missing Data

### 5.3.1. Pharmacokinetic Data

Methods to handle missing PK data are described below.

#### **Concentrations Below the Limit of Quantification:**

In all data presentations (except listings), concentrations below the limit of quantification (BLQ) will be set to zero. (In listings BLQ values will be reported as “<LLQ”, where LLQ will be replaced with the value for the lower limit of quantification.).

#### **Deviations, Missing Concentrations and Anomalous Values:**

In summary tables and plots of median profiles, statistics will be calculated having set concentrations to missing if 1 of the following cases is true:

1. A concentration has been collected as ND (ie, not done) or NS (ie, no sample).
2. A deviation in sampling time is of sufficient concern or a concentration has been flagged anomalous by the pharmacokineticist.

Note that summary statistics will not be presented at a particular time point if more than 50% of the data are missing.

An anomalous concentration value is one that, after verification of bioanalytical validity, is grossly inconsistent with other concentration data from the same individual or from other participants. For example, a BLQ concentration that is between quantifiable values from the same dose is considered as anomalous. Anomalous concentration values may be excluded from PK analysis at the discretion of the PK analyst.

## PK Parameters:

Actual PK sampling times will be used in the derivation of PK parameters. If a PK parameter cannot be derived from a participant's concentration data, the parameter will be coded as NC (ie, not calculated). (Note that NC values will not be generated beyond the day that a participant discontinues). In summary tables, statistics will be calculated by setting NC values to missing; and statistics will be presented for a particular dose with  $\geq 3$  evaluable measurements.

If an individual participant has a known biased estimate of a PK parameter (due for example to an unexpected event such as vomiting before all the compound is adequately absorbed from the gastrointestinal tract), this will be footnoted in summary tables and will not be included in the calculation of summary statistics or statistical analyses.

